#### 6.4.2.3 Time to Sustained Clinical Resolution

Sustained clinical resolution is defined in Section 4.2.

Same statistical methods as those described in section 6.4.1 will be used to analyze the time to sustained clinical resolution.

### 6.4.3 Other Secondary Analysis

#### **6.4.3.1 Time to Viral Clearance Based on PCR Test for SARS-CoV-2**

Each subject will be tested to determine if the subject has COVID-19 by obtaining a PCR or rapid antigen test as it confirms the presence of SARS-CoV-2. A subject will be considered to no longer have COVID-19 if two consecutive PCRs do not detect SARS-CoV-2. Time to viral clearance using PCR test for SARS-CoV-2, as assessed using the saliva and using the nasal swab, will be calculated as date of the first negative PCR test for SARS-CoV-2 – date of randomization + 1. Subjects who did not obtain two consecutive negative PCRs will be censored at the date of study completion.

Same statistical methods as those described in section 6.4.1 will be used to analyze the time to viral clearance.

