### **7.1.4. Viral Clearance as Measured Based on PCR Test for SARS-CoV-2**

Each patient will be tested to determine if the patient has COVID-19 by obtaining a PCR or rapid antigen test as long as it confirms the presence of SARS-CoV-2 per Schedule of Assessments ([Appendix 4](#)). Saliva and nasal secretions will be collected as noted in the schedule of assessments and assessed centrally by PCR for the presence or absence of SARS-CoV-2. A patient will be considered to no longer have COVID-19 if two consecutive PCRs do not detect SARS-CoV-2. Time to viral clearance using PCR test for SARS-CoV-2 will be the period between randomization and the date of the first negative PCR test for SARS-CoV-2.

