- a. Screening/Baseline assessments may all be performed on the same calendar day and should be performed at the study site or as a home visit within 72 hours of first dose. Baseline assessments that are also performed at Screening do not need to be repeated if on the same calendar day. Study drug should be dispensed at the Screening/Baseline visit and only taken after the Day 1 virtual visit confirming the positive COVID-19 test has occurred. If the PCR test is negative or laboratory results exclude the patient, they will not take the first dose of study drug and be withdrawn from the study.
- b. Patients will be randomized to receive either 900, 1800, or 3600 mg of dalcetrapib treatment or placebo.
- c. The entry testing is performed locally based on testing methods available at the site, such as PCR or rapid antigen test.
- d. Patients must have at least two mild to moderate signs or symptoms of COVID-19, as described in the inclusion criteria, with onset within 5 days of first dose on Day 1. Symptoms will be assessed daily for the first 10 days, then at Day 14 and Day 28 and as clinically indicated.
- e. Dates of change in WHO scale status between visits will be recorded over the course of the 28-day study period.
- f. SARS-CoV-2 viral loads will be obtained by both saliva (Oragene) and mid-turbinate nasal swab self-collected under supervision of a healthcare professional at Screening/Baseline, Day 1, Day 3, Day 5, Day 7, Day 10, and Day 28.
- g. Two PK samples will be collected on Day 10, one at predose and one at postdose in a sampling window of 0-2, 2-4, 4-6, 6-10, or 10-24 hours postdose. Patients will be evenly randomized to one of the sampling windows on Day 10.
- h. Study drug is self-administered as once daily oral tablets on Days 1 to 10.
- i. In case of screen failure only.

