#### **6.2.2.2 Censoring**

Severity Symptom Score: For time to resolution, a patient will be censored if the patient has not had the required time point assessment if not due to death. If patient has died or received another antiviral therapy prior to the assessment endpoint, then the patient will be considered as having a moderate or severe COVID-19 symptom for all COVID-19 symptoms and imputed to maximum severity score at the assessment day.

Viral Clearance: For time to viral clearance, a patient will be censored if the patient has not had the required time point assessment.

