**Reporting windows for the classification of the visit identifiers for symptom score and viral load\***

VISIT**	SCHEDULED WINDOW (± DAYS)	DIFFERENCE BETWEEN DATE OF ASSESSMENT AND DATE OF 1 ST DOSE
*Screening	---	<0
*DAY 1	---	0
DAY 2	---	1
DAY 3	---	2
DAY 4	---	3
DAY 5	---	4
DAY 6	---	5
DAY 7	---	6
DAY 8	---	7
DAY 9	---	8
DAY 10	---	9
Follow-up visit 1 (DAY 14)	±2	11 to 15
Follow-up visit 2 (DAY 28/EOS)	±2	25 to 29

\*Screening and Day 1 will not be reported separately but will be used to classify the baseline visit as detailed above.

\*\*Viral loads are presented ONLY at baseline, Day 3, Day 5, Day 7, Day 10 & Day 28/EOS.

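### Viral clearance needs two consecutive negative PCRs, but its date is not tied to that pair, and a first negative at Day 28 can never count as an event

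*SAP*

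**What the plan says.** SAP 6.4.3.1 sets the criterion: "A subject will be considered to no longer have COVID-19 if two consecutive PCRs do not detect SARS-CoV-2". The time is then the "date of the first negative PCR test for SARS-CoV-2" minus the randomization date, plus one day. Anyone without a pair is handled by a third sentence: "Subjects who did not obtain two consecutive negative PCRs will be censored at the date of study completion". Protocol 7.1.4 has the same criterion and measures "the period between randomization and the date of the first negative PCR test for SARS-CoV-2".

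SAP 6.2.2.2 adds a general rule, without a censoring date: "For time to viral clearance, a patient will be censored if the patient has not had the required time point assessment".

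The footnotes to the Protocol's Table 5 place samples at "Screening/Baseline, Day 1, Day 3, Day 5, Day 7, Day 10, and Day 28". The note under the SAP's Appendix 2 table says: "Viral loads are presented ONLY at baseline, Day 3, Day 5, Day 7, Day 10 & Day 28/EOS". Neither document schedules a PCR sample between Day 10 and Day 28, or after Day 28.

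The analysis follows SAP 6.4.1: log-rank tests, and simple medians in which censored subjects are given 29 days. The endpoint is derived separately for saliva and for nasal swab.

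**The concern.** There are two separate problems.

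- **Dating.** The event is defined by a pair of tests and dated by a single test. Nothing says that the single test is the first of the pair. A programmer who takes the sentence at its word would use the first negative ever recorded, even when a positive follows it. SAP Appendix 1 spells out what a relapse does to the symptom date; there is no such rule for PCR.
- **Late clearance.** A negative at the last scheduled visit has no later sample to confirm it. A patient positive on Day 10 and negative on Day 28 therefore cannot have an event and is pooled with patients who never clear.

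At stake are the event dates of intermittent clearers, the reported proportion cleared, and the events available to the log-rank test. The endpoint is one of the other secondary ones, but SAP section 1 gives virology more weight than before in judging proof of concept. An open dating rule also leaves a choice that could be made after unblinding.

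**Working it through.** The documents give no event count or power for viral clearance, so there is no planned figure to reproduce.

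**1. Patterns.** Take post-baseline Days 3, 5, 7, 10 and 28, each negative (N) or positive (P). There are 2^5 = 32 patterns, and 19 contain two consecutive negatives. The first negative ever and the first negative of the first pair differ in four of them:

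| D3 | D5 | D7 | D10 | D28 | First negative ever | First of the pair | Gap (days) |
|---|---|---|---|---|---|---|---|
| N | P | N | N | N | Day 3 | Day 7 | 4 |
| N | P | N | N | P | Day 3 | Day 7 | 4 |
| N | P | P | N | N | Day 3 | Day 10 | 7 |
| P | N | P | N | N | Day 5 | Day 10 | 5 |

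A confirmed event can fall only on Day 3, 5, 7 or 10. Eight of the 32 patterns are positive at Day 10 and negative at Day 28. In none of them does the Day 28 negative produce an event.

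**2. Share misdated under the literal reading.** Assumptions, none from the documents: exponential clearance with 35% still positive at Day 10; a false-negative chance f per test before true clearance, independent between tests; no positives after clearance; time on the study-day scale.

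The rate is −ln(0.35)/10 = 0.105 per day. Of all patients, 0.112 clear between Days 5 and 7, 0.130 between Days 7 and 10, 0.297 between Days 10 and 28, and 0.053 after Day 28. Adding the four patterns:

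misdated = f(1−f)[0.112 + 0.130f + 0.35f²] + 2f(1−f)²[0.130 + 0.297f + 0.053f²]

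At f = 0.10: 0.09 × 0.1285 + 0.162 × 0.1598 = 0.0116 + 0.0259 = 0.037 of all patients. The confirmed share, summed over patterns in the same way, is 0.687, so 0.0375/0.687 = 5.5% of confirmed clearers.

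| f | Misdated, all patients | Confirmed | Misdated, of confirmed | Lone Day 28 negative, no pair |
|---|---|---|---|---|
| 0 | 0 | 65.0% | 0 | 29.7% |
| 5% | 1.9% | 66.7% | 2.8% | 28.3% |
| 10% | 3.7% | 68.7% | 5.5% | 26.7% |
| 20% | 7.3% | 73.4% | 10.0% | 22.8% |

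**3. Late clearers.** With f = 0, the lone Day 28 share is 0.350 − 0.053 = 0.297. The analysis would report 65% cleared, although 65% + 29.7% = 94.7% are negative at Day 28.

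**4. Medians.** If 65% have cleared by Day 10, the median lies at or before Day 10. Giving late clearers 28 days instead of 29 does not move it. In simulated trials (52 versus 104 patients, hazard ratio 1.4, no false negatives) the arm medians were unchanged in 98% of trials for placebo and 100% for the two highest doses combined.

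**5. Power.** Simulated log-rank test at two-sided 0.20, 52 versus 104 patients. The hazard ratio of 1.4 is borrowed from the symptom endpoint for illustration. No false negatives; 600 runs per row; Monte Carlo error about 2 points; shares pooled over arms.

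| Placebo median (days) | Confirmed by a pair | Lone Day 28 negative | Power, pair required | Power, lone Day 28 counted |
|---|---|---|---|---|
| 5 | 82% | 17% | 0.66 | 0.69 |
| 7 | 71% | 26% | 0.63 | 0.68 |
| 10 | 58% | 33% | 0.58 | 0.69 |
| 14 | 47% | 36% | 0.53 | 0.67 |

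Under the 35% assumption, the Day 28 rule costs about 4 to 6 points of power. Literal dating costs 0 to 3 points at false-negative rates up to 20%.

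**The case against.** The best reply on dating is that the two-negative criterion stands immediately before the dating sentence in both documents. Read together, they can mean the first negative of the qualifying pair, which is the usual convention. On that reading no date is wrong. This stands: the dating problem is an ambiguity, and a reader who concludes that clearance times are necessarily wrong goes further than the text allows. It does not remove the need for the missing words.

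A reader might also count Day 1 as follow-up. The readings then differ in 12 of 43 confirmed patterns, by up to 9 days, and the misdated shares rise to about 5%, 10% and 18%. SAP 6.4.2.1 and Appendix 2 treat Day 1 as the pre-dose baseline, so these larger figures are not supported. Collection is also supervised by a healthcare professional, and no false-negative rate is given.

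On late clearers, a reader might infer that they receive wrong times or that the medians are wrong. They are right-censored at study completion and set to 29 days for the median, close to the Day 28 visit. The medians hold as long as most patients clear by Day 10. Day 28 virology is also not lost to the trial, because the key secondary viral-load model includes that visit.

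Finally, the Protocol and SAP do not contradict each other: they share the criterion and the dating rule. The endpoint carries no stopping decision, and the SAP makes no multiplicity adjustment. All of this limits the weight of the point. It does not answer the fact that a first negative at Day 28 cannot be an event.

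**Conclusion.** The point holds in two limited parts.

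First, both documents leave the dating test untied to the confirming pair. The literal reading would place some clearances 4 to 7 days early, ahead of a documented positive. The share affected is about 3% to 10% of confirmed clearers at assumed false-negative rates of 5% to 20%, zero without false negatives, and zero if the first of the pair is meant.

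Second, the sampling days alone, with no assumption, mean that no event can be dated after Day 10 and that first negatives at Day 28 are censored with patients who never clear. The size does rest on an assumption: about 23% to 30% of patients if 35% are positive at Day 10. The consequences are lost events and an understated cleared proportion. The power loss is modest with fast clearance and larger with slow clearance (0.53 against 0.67 at a 14-day placebo median).

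Both should be settled before unblinding.

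**What to change.** In SAP 6.4.3.1 and Protocol 7.1.4:

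- Date clearance at the first negative of the first two consecutive negative PCRs.
- Define the time-to-event endpoint as confirmed clearance through Day 10, with the Day 28 sample used to confirm a Day 10 negative.
- Report the proportion PCR-negative at Day 28 by arm, separately for saliva and nasal swab.
- Present any analysis that counts a lone Day 28 negative as clearance as a sensitivity analysis only.

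The cost is a short text change in each document and one extra summary. The main analysis will still not count late clearers, so the lost events are not recovered there; the change makes plain what is measured and shows late negativity beside it. Counting a lone Day 28 negative in the main analysis would recover those events, but it drops the confirmation that both documents require, and such a negative is unconfirmed. It is therefore a trade-off and not a correction.

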#### **6.4.3.2 Time to Complete Clinical Resolution (excluding cough, sense of taste and smell)**

Complete clinical resolution (excluding cough, sense of taste and smell) is defined in Section 4.2.

Same statistical methods as those described in section 6.4.1 will be used to analyze the time to complete clinical resolution (excluding cough, sense of taste and smell).

#### **6.4.3.3 Time to Complete Clinical Resolution**

Time to complete clinical resolution is defined in Section 4.2

Same statistical methods as those described in section 6.4.1 will be used to analyze the time to complete clinical resolution.

#### **6.4.3.4 Change from Baseline in COVID-19 Total Symptom Score**

COVID-19 total symptom score will be summarized by treatment group using descriptive statistics (N, mean, median, standard deviation, minimum, and maximum) for each visit as well as for changes from baseline where an 80% CI will also be presented.

Mean changes from baseline will be analyzed using a repeated measures ANCOVA model including effects of treatment, visit (Day5, Day10, Day14 & Day28/EOS), and treatment-by-visit interaction, as well as baseline value of total symptom score and baseline value of total symptom score-by-visit-interaction. An unstructured covariance structure will be used to model the within-patient errors and the Kenward-Roger approximation will be used to estimate denominator degrees of freedom. The combined two highest treatment groups will be compared to placebo in addition to the comparison of individual doses at the following study visits (Day5, Day10, Day14 and Day 28/EOS).

Symptom scores were either reported electronically by the subject or by the site through telephone calls. Except for the assessments done at screening reported in the eCRF, no visit identifiers were attached to these evaluations, only the date of the assessment. Therefore, similar to viral load, the day of assessment of the symptom scores will be classified into visit identifiers as per the algorithm presented in Appendix 2. This will ensure that Day X for symptom score will correspond to Day X for viral load.

A plot of mean change from baseline in COVID-19 total symptom score with 80% CI at each study visit on the ITT population will be presented (Section 7, Figure 6).

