#### ***8.4.2.2. Change from Baseline in COVID-19 Symptom Severity Score***

COVID-19 total symptom severity score will be summarized by treatment group using descriptive statistics (N, mean, median, standard deviation, minimum, and maximum) for each visit as well as for changes from baseline (N, mean, standard error, CI). A Mixed-Effect Model Repeated Measure (MMRM) will be performed to analyze the average difference between treatment groups over 28 days and at the designated assessment days.

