## 2 STUDY DESCRIPTION

### 2.1 Study Design

This is a randomized, double-blind, multicenter Phase 2a proof-of-concept study in outpatients with confirmed, mild to moderate, symptomatic COVID-19. Electronic informed consent must be obtained from all patients or their legally authorized representative during screening before any study-related procedures are performed. The Screening/Baseline assessments may be performed at the study site or as a home visit.

A total of 208 patients will be randomized to receive 900, 1800, or 3600 mg of dalcetrapib or placebo once daily (52 patients to each of 900 mg, 1800 mg, 3600 mg and placebo) for 10 days. Patients will be randomized and receive first dose of study drug within 72 hours of receiving a positive PCR or Point-of-care test for SARS-CoV-2. Patients need to have at least two of the 14 common COVID-19-related symptoms described in the inclusion criteria rated as mild or moderate, as evaluated by ePRO assessment or eCRF. Symptoms will be assessed at each study visit daily for the first 10 days, then at Day 14 and Day 28, and as clinically indicated. Symptoms will be evaluated as absent, mild, moderate, or severe depending on their impact on activities of daily living. SARS-CoV-2 viral loads will be obtained by both saliva (Oragene) collection and mid-turbinate nasal swab self-collection under supervision of a healthcare professional (virtual or home visit) at Screening/Baseline, Day 1, Day 3, Day 5, Day 7, Day 10, and Day 28. Patients who require hospitalization after initiation of study treatment will be followed for safety assessment through Day 28.

The study will be overseen by an independent Data Monitoring Committee (DMC). The DMC will review the safety data throughout the study. The DMC and Sponsor will review efficacy data at the interim analysis and at the end of the study. A DMC Charter, which includes detailed processes, will be prepared. One interim analysis will be conducted once 120 patients have a follow-up time of 28 days.

All patients will be closely monitored for adverse events (AEs) from informed consent for at least 18 days after the final dose of study treatment (until Day 28±2). Patients who withdraw early from the

study treatment will have follow-up phone calls to collect safety data until End of Study on Day 28±2. On days of laboratory assessments and PK sample collection, outpatient subjects may have a home visit.

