## 2.2 Study Objectives

The primary efficacy objective of the study is:

- To evaluate the time to sustained clinical resolution of symptoms (excluding cough, sense of smell and taste) in patients with confirmed, mild to moderate, symptomatic COVID-19 treated with dalcetrapib.

The key secondary efficacy objectives of the study are:

- To evaluate change from baseline in log10 viral load
- To evaluate the time to sustained clinical resolution of symptoms in patients with confirmed, mild to moderate, symptomatic COVID-19 treated with dalcetrapib.

Other secondary efficacy objectives of the study are:

- To evaluate the time to viral clearance using SARS-CoV-2 polymerase chain reaction (PCR)
- To evaluate time to complete clinical resolution of symptoms (excluding cough, sense of smell and taste), defined in the same way as the primary endpoint, but considering that all symptoms must resolve to a score of 0 for 72 hours
- To evaluate time to complete clinical resolution of symptoms considering that all symptoms must resolve to a score of 0 for 72 hours
- To evaluate the change from baseline in COVID-19 total symptom score at all collected time points
- To evaluate the WHO Clinical Outcome Scale (9-point scale) at Day 3, Day 5, Day 10, Day 14 and Day 28
- To evaluate the rate of hospitalization through Day 28
- To evaluate the rate of progression to oxygen therapy through Day 28
- To evaluate the duration of hospitalization
- To evaluate the mortality rate by Day 28

The safety objective of the study is:

- To assess the safety and tolerability of dalcetrapib active doses compared to placebo in patients with COVID-19

The pharmacokinetics (PK) objective of the study is:

- To evaluate the PK of dalcetrapib in patients with COVID-19. The methodology for PK analysis will not be documented in this SAP but in a separate PK plan.

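### The SAP's comparisons of total symptom score use only Days 5, 10, 14 and 28 and omit, without a stated reason, the 28-day average difference that the protocol specifies

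*SAP*

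**What the plan says.** **Collection.** Protocol Appendix 4 (Table 5, footnote d) states: "Symptoms will be assessed daily for the first 10 days, then at Day 14 and Day 28 and as clinically indicated". SAP 2.1 has the same schedule. SAP Appendix 2 uses Day 1 as baseline where available and gives every day from Day 2 to Day 10 its own window.

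**Objective.** SAP 2.2 lists among the other secondary objectives: "To evaluate the change from baseline in COVID-19 total symptom score at all collected time points".

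**Protocol analysis.** Protocol 8.4.2.2 plans a mixed model for repeated measures "to analyze the average difference between treatment groups over 28 days and at the designated assessment days". It does not list the designated days, and it does not say which scores enter the average or with what weights.

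**SAP analysis.** SAP 6.4.3.4 fits a baseline-adjusted repeated-measures model with "visit (Day5, Day10, Day14 & Day28/EOS" as the visit effect and an unstructured covariance. The two highest doses combined, and the individual doses, are compared with placebo "at the following study visits (Day5, Day10, Day14 and Day 28/EOS". No averaged contrast is specified. Descriptive statistics are wider: they are planned "for each visit as well as for changes from baseline where an 80% CI will also be presented", with a plot of mean change by visit.

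**Testing and precedence.** SAP 6.2 sets all tests at two-sided 0.20, and SAP 6.2.3 makes no multiplicity adjustment. Under SAP section 1 the SAP prevails where it differs from the protocol.

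**The concern.** The protocol's summary estimate disappears between the two documents. The SAP Revision History does not mention it. SAP section 1 explains why symptom endpoints carry less weight and why cough, taste and smell are left out of some analyses. Neither reason accounts for removing an average over time. Because the SAP prevails, the average will not be produced unless the SAP is edited.

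Two consequences follow.

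- The endpoint has no single answer. A reader gets four visit-specific p-values per comparison and no prespecified way to combine them.
- Nothing before Day 5 of a 10-day course is compared between arms on this endpoint. The viral-load model (SAP 6.4.2.1) and the WHO-scale tests (SAP 6.4.3.5) both include Day 3. SAP 6.4.3.4 itself says that its windows line up symptom days with viral-load days, yet it omits Day 3.

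**Working it through.** The documents give no power figure, SD or within-patient correlation for this endpoint, so there is no plan figure to reproduce. The only sizing figure, 127 events, belongs to symptom resolution. Correlations are therefore assumed: exchangeable 0.4–0.8, or autoregressive with per-day correlation 0.7–0.95. Equal variance at each visit is also assumed.

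**1. Time points.** Days 2–10 give 9, and Days 14 and 28 give 2 more, so 11 post-baseline. The model uses 4. An unstructured matrix for k visits has k(k+1)/2 parameters: 10 for k = 4, 21 for k = 6, 66 for k = 11.

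**2. Do the planned visit contrasts lose precision?** With complete data and an unstructured matrix, the Day 10 standard error (SE) is the same with 4 or 11 visits (ratio 1.000). If 10–20% of Day 10 scores are missing, the four-visit SE is 1.004–1.037 times the 11-visit SE. The loss is nil to small.

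**3. What would a 28-day average gain over one visit?** Take Days 3, 5, 7, 10, 14 and 28 with trapezoid weights from Day 1. The half-interval sums are 2, 2, 2.5, 3.5, 9 and 7, total 26. The remaining 1 of 27 days falls on Day 1, where change is zero. Dividing by 26 makes the weights sum to 1, so

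Σw² = (4 + 4 + 6.25 + 12.25 + 81 + 49)/676 = 156.5/676 = 0.2315.

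For exchangeable correlation ρ, the SE of the average divided by the SE of one visit is:

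- without baseline adjustment: √[(1−ρ)Σw² + ρ]. At ρ = 0.4, √0.539 = 0.73. At ρ = 0.8, √0.846 = 0.92.
- with baseline adjustment, as in the SAP model: √[(Σw² + ρ)/(1 + ρ)]. At ρ = 0.4, √0.451 = 0.67. At ρ = 0.8, √0.573 = 0.76.

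The autoregressive cases use the matrix form √(w′Aw / A₁₀), where A is the (baseline-adjusted) covariance matrix and A₁₀ its Day 10 variance.

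| Assumed correlation | Unadjusted | Baseline-adjusted |
|---|---|---|
| Exchangeable 0.4 | 0.73 | 0.67 |
| Exchangeable 0.6 | 0.83 | 0.72 |
| Exchangeable 0.8 | 0.92 | 0.76 |
| Autoregressive 0.7 | 0.54 | 0.54 |
| Autoregressive 0.8 | 0.59 | 0.58 |
| Autoregressive 0.9 | 0.71 | 0.68 |
| Autoregressive 0.95 | 0.82 | 0.80 |

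Over 4, 6 or 11 visits and equal or time weights, the full range is 0.52–0.92.

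**4. Do the daily scores sharpen a time-weighted average?** With plain trapezoid weights that count Day 1 as zero change, the four-visit SE is 0.97–1.00 of the 11-visit SE, so there is no gain. Those weights sum to 0.926 for 4 visits and 0.981 for 11. If both sets are rescaled to sum to 1, the baseline-adjusted four-visit SE is 1.03–1.08 times the 11-visit SE, and the six-visit SE is only 1.01–1.02 times. The reason is that Days 14 and 28 carry 0.333 + 0.259 = 59% of the plain 11-visit weight. An equal-weight average gains more (ratio 1.02–1.32 over a slightly wider set of assumed correlations), but 9 of its 11 scores fall in Days 2–10.

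**5. Four tests instead of one.** If there is no effect, the chance that at least one of the four visit tests gives p < 0.20 is about 39–54% for test statistics correlated at exchangeable 0.8–0.4, and 47–58% for autoregressive 0.95–0.7. After baseline adjustment it is 51–59%. The independence limit is 1 − 0.8⁴ = 59%. One prespecified average keeps 20% per comparison. With the combined doses and three single doses, the SAP has 4 × 4 = 16 visit tests.

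**The case against.** The strongest reply is that the SAP openly demotes symptom endpoints, prevails over the protocol, declares that it does not adjust for multiplicity, and fixes its four days in advance. This is one of the other secondary endpoints, with no stated power. Early symptom change is not ignored either: the resolution endpoints use the Day 1–10 records through SAP Appendix 1. All of that stands, and it keeps the point small. It does not explain why the average was removed.

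Four stronger readings are tempting, and the documents do not support them.

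- A reader might infer that the SAP contradicts its own objective. The summaries with 80% intervals and the plot are not limited to the four model days, so the objective is met descriptively. Only the comparisons fall short.
- A reader might infer that the planned tests lose precision because daily scores are left out. Step 2 shows that they do not with complete data.
- A reader might infer that the protocol's average used every daily score. Protocol 8.4.2.2 does not say so.
- A reader might quote the gain for a mean over Days 2–10. Neither document plans that quantity.

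A 28-day average also has a limit. For an effect that peaks at Day 5 and is gone by Day 9, the time-weighted 11-visit average is only about 15% of the peak. The average therefore cannot replace early visit contrasts.

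**Conclusion.** The point holds as a minor improvement. SAP 6.4.3.4 drops the protocol's averaged contrast without a reason specific to it, compares no arms before Day 5 on this endpoint, and leaves four unadjusted tests per comparison with no overall estimate.

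The cost is the absent average. Its SE would be 0.52–0.92 of a single visit's over the assumed range, or 0.54–0.80 for the six-visit, time-weighted, baseline-adjusted version in the fix. A smaller SE means more power only if the effect is broadly similar across visits. These figures rest on assumed correlations, equal variances and complete data. The planned visit contrasts are sound as they are, and daily scores add little or nothing to a time-weighted average. The primary endpoint and the sample size are not affected.

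**What to change.** In SAP 6.4.3.4:

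- Restore the protocol's 28-day average as one contrast per comparison from the same model, with its weights written down. Time weights are one example; say whether they are rescaled to sum to 1.
- Add the scheduled Day 3 and Day 7 visits to the model and the contrasts, giving six visits and 21 covariance parameters.
- Name a fallback covariance structure for non-convergence. It should suit uneven spacing; first-order ante-dependence, with 2 × 6 − 1 = 11 parameters, is one candidate.
- Keep the visit-specific contrasts as supporting results.
- State why the SAP differs from Protocol 8.4.2.2 wherever it still does.

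The full 11-day model is optional: it needs 66 parameters and hardly improves the time-weighted average. If the sponsor prefers the present four days, the alternative is to give the reason for omitting the average and to word the SAP 2.2 objective so that comparisons are limited to those days.

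The cost is SAP text, one more contrast per comparison and a somewhat larger covariance matrix. No new data are needed. The weights and days should be fixed before those choosing them see unblinded results.
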